4.7.2. Vaccinations

The vaccination risk mitigation strategy detailed in the table above recommends that all necessary vaccinations should be administered if possible no later than 30 days prior to day 0 and requires that no live vaccine be given from 30 days prior to day 0 until the end of the general follow up period or IFU, if appropriate. In determining which vaccinations are necessary, investigators should follow guidelines such as the EULAR recommendations for vaccination in adult patients with autoimmune inflammatory rheumatic diseases ([van Assen](#), 2011). If indicated for standard of care, non live vaccines (e.g., inactivated influenza vaccines) may be administered while on study based on an assessment of the benefit:risk (e.g.: theoretical risk of decreased responsiveness).

4.7.3. Benefit Assessment

This study provides an opportunity for subjects with moderate to severely active Sjögren's syndrome to benefit from a potentially disease modifying regimen that may stop B-cell mediated autoimmune damage, alleviate glandular as well as constitutional symptoms, and ameliorate extra-glandular target organ manifestations. Additionally this

study is designed for active Sjögren's syndrome patients who are not experiencing relief despite their current medications, including topical symptomatic medications, oral muscarinic agonists, steroids and hydroxychloroquine (which are permitted in all arms) to benefit from the addition of potentially beneficial biological therapy.

4.7.4. Overall Benefit:Risk Conclusion

Taking into account the measures that will be implemented to minimize risk to subjects participating in this study, the potential risks associated with belimumab and rituximab are justified by the anticipated benefits that may be afforded to patients with Sjögren's syndrome who choose to participate in this trial.

5. SELECTION OF STUDY POPULATION AND WITHDRAWAL CRITERIA

Specific information regarding warnings, precautions, contraindications, adverse events, and other pertinent information on the GSK investigational product or other study treatment that may impact subject eligibility is provided in the IB/IB supplement and product label.

Deviations from inclusion and exclusion criteria are not allowed because they can potentially jeopardize the scientific integrity of the study, regulatory acceptability or subject safety. Therefore, adherence to the criteria as specified in the protocol is essential.

5.1. Inclusion Criteria

A subject will be eligible for inclusion in this study only if all of the following criteria apply:

AGE
1. Age \geq 18 years, at the time of signing the informed consent.

TYPE OF SUBJECT AND DIAGNOSIS INCLUDING DISEASE SEVERITY
2. Documented Primary Sjögren's Syndrome by American European Consensus Group criteria including: 
 - either SS-A or SS-B positive. 3. Baseline unstimulated salivary flow >0.0 mL/min or evidence of glandular reserve function (stimulated baseline salivary flow >0.05 mL/min). 4. Symptomatic oral dryness ($\geq 5/10$ on subject completed Numeric Response Scale) 5. Systemically active disease, ESSDAI ≥ 5 points.

OR (for sites in ITALY ONLY)

Systemically active disease, ESSDAI ≥ 5 points and with at least:

- a) 1 extraglandular domain moderate,

OR
 b) 2 extraglandular domains low.

SEX

6. Male and female subjects; females of child bearing potential are eligible if using effective contraception:

Female subject is eligible to participate if she is not pregnant (as confirmed by a negative urine human chorionic gonadotropin (hCG) test), not lactating, and at least one of the following conditions applies:

a. Non-reproductive potential defined as:

- Pre-menopausal females with one of the following:

- Documented tubal ligation
- Documented hysteroscopic tubal occlusion procedure with follow-up confirmation of bilateral tubal occlusion
- Hysterectomy
- Documented Bilateral Oophorectomy

- Postmenopausal defined as 12 months of spontaneous amenorrhea [in questionable cases a blood sample with simultaneous follicle stimulating hormone (FSH) and estradiol levels consistent with menopause (refer to laboratory reference ranges for confirmatory levels)]. Females on hormone replacement therapy (HRT) and whose menopausal status is in doubt will be required to use one of the highly effective contraception methods if they wish to continue their HRT during the study; otherwise, they must discontinue HRT to allow confirmation of post-menopausal status prior to study enrolment.

b. Reproductive potential and agrees to follow one of the options listed below in the GSK Modified List of Highly Effective Methods for Avoiding Pregnancy in Females of Reproductive Potential (FRP) requirements from 30 days prior to the first dose of study medication up to Week 68 after Day 0.

GSK Modified List of Highly Effective Methods for Avoiding Pregnancy in Females of Reproductive Potential (FRP)

This list does not apply to FRP with same sex partners, when this is their preferred and usual lifestyle or for subjects who are and will continue to be abstinent from penile-vaginal intercourse on a long term and persistent basis.

- Contraceptive subdermal implant that meets the SOP effectiveness criteria including a <1% rate of failure per year, as stated in the product label
- Intrauterine device or intrauterine system that meets the SOP effectiveness criteria including a <1% rate of failure per year, as stated in the product label
- Combined estrogen and progestogen oral contraceptive

- Injectable progestogen
- Contraceptive vaginal ring
- Percutaneous contraceptive patches
- Male partner sterilization with documentation of azoospermia prior to the female subject's entry into the study, and this male is the sole partner for that subject.

These allowed methods of contraception are only effective when used consistently, correctly and in accordance with the product label.

The investigator is responsible for ensuring that subjects understand how to properly use these methods of contraception.

INFORMED CONSENT

7. Ability to understand and comply with the protocol-required procedures and provision of informed consent.

OTHER CRITERIA

8. For **FRANCE ONLY**, a subject will be eligible for inclusion in this study if he /she is either affiliated to or beneficiary of a social security category. It is the investigator's responsibility to ensure and to document (in source document - patient notes) that the patient is either affiliated to or beneficiary of a social security category.

5.2. Exclusion Criteria

A subject will not be eligible for inclusion in this study if any of the following criteria apply:

CONCURRENT CONDITIONS/MEDICAL HISTORY

1. Diagnosis of secondary Sjögren's syndrome.
2. Active life-threatening or organ-threatening complications of SS disease at the time of screening based on treating physician evaluation including but not restricted to (a) vasculitis with renal, digestive, cardiac, pulmonary or CNS involvement characterized as severe, (b) active CNS or PNS involvement requiring high dose steroids, (c) severe renal involvement defined by objective measures, (d) lymphoma.
3. History of major organ transplant (including hematopoietic stem cell transplant).
4. History of malignancy within past 5 years [with the exception of adequately treated: (a) cervical carcinoma Stage 1B or less, (b) non-invasive basal cell and squamous cell skin carcinoma].
5. History of infection requiring long term systemic therapy including: (a) history of positive HIV serology, (b) positive serology for Hepatitis C (HCV), (c) positive serology for Hepatitis B (HB), defined as: (i) HB surface antigen positive (HBsAg+)

OR (ii) HB core antibody positive (HBcAb+).

6. Previous serious opportunistic or atypical infections or hospitalization for treatment of infection within 364 days of Day 0 or use of parenteral (IV or IM) antibacterials, antivirals, anti-fungals, or anti-parasitic agents within 364 days of prior to Day 0.
7. Patients in a severely immunocompromised state.
8. History of an anaphylactic reaction to parenteral administration of contrast agents, human or murine proteins or monoclonal antibodies.
9. History of significant medical illness (or planned surgical procedure) which in the opinion of the investigator would interfere with the study procedures and / or assessments - including but not limited to IgG4 disease or prior head or neck irradiation.
10. Severe heart failure (New York Heart Association, Class IV) or other severe, uncontrolled cardiac disease.
11. Tuberculosis (TB), defined as: (a) prior history of TB infection, (b) suspicion of TB infection or (c) current TB infection.
12. At risk of suicide, as indicated by a lifetime history of attempted suicide or significant suicidal ideation over the 6 months prior to the screening visit; or, if in the Investigator's judgment, the subject is at risk for a suicide attempt.
13. Neurological findings consistent with Progressive Multifocal Leukoencephalopathy (PML) - not otherwise explained - or confirmed PML.
14. Electrocardiogram (ECG) showing a clinically significant abnormality at Screening or showing an average QTcB or QTcF interval ≥ 450 msec (≥ 480 msec for subjects with a Bundle Branch Block) over 3 consecutive ECGs (refer to Section 7.4.5)
15. ALT $>2\times$ ULN and bilirubin $>1.5\times$ ULN (isolated bilirubin $>1.5\times$ ULN is acceptable if bilirubin is fractionated and direct bilirubin $<35\%$).
16. Current or chronic history of liver disease, or known hepatic or biliary abnormalities (with the exception of Gilbert's syndrome or asymptomatic gallstones)

CONCOMITANT MEDICATIONS

17. Use of systemic immunosuppressive or immunomodulatory agents including methotrexate, azathioprine, leflunomide, mycophenolate (including mycophenolate mofetil, mycophenolate mofetil hydrochloride, and mycophenolate sodium), mizoribine, calcineurin inhibitors (e.g., tacrolimus, cyclosporine), sirolimus, 6-mercaptopurine, or thalidomide) within 60 days prior to Day 0.
18. Have received cyclophosphamide within 180 days prior to Day 0.
19. Have received anti-BLyS, anti-CD 20, anti-CD22 or anti-CD52 or any other B-cell depleting agent within 364 days prior to Day 0.
20. Have received abatacept or any biologic agent within 180 day prior to Day 0
21. Have received IVIG or plasmapheresis within 90 days prior to Day 0.
22. Have received oral steroid >10 mg prednisone equivalent/day within 30 days prior to

Day 0 or oral steroid >20 mg prednisone equivalent / day for a minimum of two consecutive weeks within 60 days prior to Day 0. Have received parenteral steroid within 60 days prior to Day 0.

23. Have received a live vaccine within 30 days of Day 0.
24. Current participation in any other interventional trial.
25. Planned blood donation during the treatment and follow up periods of the study.

RELEVANT HABITS

26. Subjects who are unable or unwilling to administer, or to have a caregiver administer subcutaneous injections.
27. Drug or alcohol abuse or dependence.

CONTRAINdications

28. History of hypersensitivity to belimumab and/or rituximab or known to have titers of human anti-mouse antibody or human anti-chimeric antibody or history of hypersensitivity reactions when treated with other diagnostic or therapeutic monoclonal antibodies.

DIAGNOSTIC ASSESSMENTS AND OTHER CRITERIA

29. Have an IgA deficiency (IgA level <10 mg/dL).
30. Any of the following screening laboratory values:
 - White blood cells (WBC) <2 x 10⁹/L
 - Neutrophils <1.5 x 10⁹/L
 - Circulating IgG < 550 mg / dL
 - Aspartate aminotransferase (AST) >2.0 times the upper limit of normal
 - Alkaline phosphatase (ALP) >1.5 times the upper limit of normal
 - Bilirubin >1.5 times the upper limit of normal (unless direct bilirubin fraction is < 35%)
 - CD 19+ B-lymphocyte counts <0.1 x 10⁹/L (<100 per CMM) (applies only to subjects previously exposed to B cell depleting therapies)
31. For **FRANCE ONLY**, subjects with legal or administrative guardianship (“tutelle” or “curatelle”), or subjects deprived of liberty, or subjects receiving psychiatric care, or subjects hospitalized in an Health and Social Establishment for purposes other than participation in this study.

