5.3. Screening/Baseline/Run-in Failures

Screen failures are defined as subjects who consent to participate in the clinical trial but are never subsequently randomized. In order to ensure transparent reporting of screen failures meet the Consolidated Standards of Reporting Trials publishing requirements, and respond to queries from Regulatory authorities, a minimal set of screen failure information is required including Demography, Screen Failure details, Eligibility Criteria, and any Serious Adverse Events.

Rescreening: Subjects who fail screening may be rescreened once at the discretion of the investigator.

Repeat assessments during the 35 day screening period: assessments (see Section 7.1), including laboratory assessments, may be repeated if determined necessary by the investigator, for example: (a) in cases of technical malfunction (e.g., loss of laboratory specimen), (b) in the event of a value close enough to the exclusionary threshold that it may reasonably lie within the degree of variability of the assay; (c) if there is reason to believe the result may be false (i.e.: contradicts recent result for the same parameter). These are repeat assessments and not rescreening events. If the original result was exclusionary and is confirmed by repeat testing, the subject will be excluded.

In the specific case of an indeterminate result from autoantibody (SS-A, SS-B) assessment during the 35 day screening period, this assessment may be repeated once. If the result from the repeat assessment is either indeterminate or negative, the subject will be excluded.

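### Exclusion criterion 15 joins its ALT and bilirubin limits with *and*, so raised ALT alone has no entry limit and the criterion's own bilirubin exception has nothing to do

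*Protocol*

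**What the plan says.** Section 5.2 excludes a subject if any one listed criterion applies. Four entries bear on the liver:

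- **Criterion 15** excludes "ALT $>2\times$ ULN and bilirubin $>1.5\times$ ULN". Its parenthesis says that isolated bilirubin >1.5xULN "is acceptable if bilirubin is fractionated and direct bilirubin" is below 35%.
- **Criterion 16** excludes on "Current or chronic history of liver disease, or known hepatic or biliary abnormalities (with the exception of Gilbert's syndrome or asymptomatic gallstones"). It names no laboratory value.
- **Criterion 30** lists laboratory values that each exclude alone: "Aspartate aminotransferase (AST) >2.0 times the upper limit of normal"; "Alkaline phosphatase (ALP) >1.5 times the upper limit of normal"; and "Bilirubin >1.5 times the upper limit of normal (unless direct bilirubin fraction is < 35"%). ALT is not on the list.
- **Criterion 9** leaves significant medical illness to the investigator's opinion, again without a laboratory threshold.

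Section 5 states that "Deviations from inclusion and exclusion criteria are not allowed". Section 5.3 adds: "If the original result was exclusionary and is confirmed by repeat testing, the subject will be excluded". Section 7.2 ties screening chemistry to the Section 5 criteria. No other part of the protocol gives a numeric ALT limit for entry. The remaining ALT thresholds are on-treatment rules (Section 5.4.5 and Appendix 2) and the SAE definition in Appendix 7.

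**The concern.** The sentence supports two readings, and its literal one does not fit its own exception. If *and* makes a joint condition, an isolated bilirubin rise can never trigger the criterion, so there is nothing to excuse. The parenthesis has work to do only if bilirubin alone could exclude, which means two separate limits. On that reading ALT >2xULN alone also excludes. On the literal reading it does not, and nothing in criterion 30 makes up for it.

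ALT is the test that governs liver safety on treatment. All six stopping rows in Appendix 2 require a raised ALT, and so does the increased-monitoring rule. The thresholds are multiples of ULN rather than of baseline, so a subject who enters with a high ALT can meet them from the outset. Section 2.2 lists autoimmune hepatitis and primary biliary cirrhosis among the extra-glandular manifestations of the disease, safety is the primary objective, and the planned arms are about 10 (placebo) and 20 (each active regimen). One avoidable liver discontinuation is therefore 1/10 = 10% or 1/20 = 5% of an arm. In a multi-national, multi-center trial with no deviations allowed, whether an isolated raised ALT is exclusionary should not depend on how a site reads one word.

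**Working it through.** The plan has no figure to reproduce here. The check lists every ALT/bilirubin pattern and applies criteria 15 and 30 under each reading.

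**Inputs (Section 5.2).** ALT: ≤2xULN or >2xULN. Bilirubin: ≤1.5xULN; >1.5xULN with direct <35%; >1.5xULN with direct ≥35%. AST and ALP are held within their criterion 30 limits. That gives 2 x 3 = 6 patterns.

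**Rules.**
- Criterion 30: exclude if bilirubin >1.5xULN and direct ≥35%.
- Criterion 15, joint: exclude if ALT >2xULN and bilirubin >1.5xULN.
- Criterion 15, separate: exclude if ALT >2xULN, or if bilirubin >1.5xULN, except isolated bilirubin with direct <35%.

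| ALT | Bilirubin | Criterion 30 | 15 joint | 15 separate | 15 + 30, joint | 15 + 30, separate |
|---|---|---|---|---|---|---|
| ≤2 | ≤1.5 | no | no | no | eligible | eligible |
| ≤2 | >1.5, direct <35% | no | no | no (exception) | eligible | eligible |
| ≤2 | >1.5, direct ≥35% | yes | no | yes | excluded | excluded |
| >2 | ≤1.5 | no | no | yes | **eligible** | **excluded** |
| >2 | >1.5, direct <35% | no | yes | yes | excluded | excluded |
| >2 | >1.5, direct ≥35% | yes | yes | yes | excluded | excluded |

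**Results.**
- Excluded: 3 of 6 on the joint reading, 4 of 6 on the separate reading. The one difference is ALT >2xULN with bilirubin ≤1.5xULN.
- The exception can only matter in the second row. Removing it changes 0 patterns on the joint reading and 1 on the separate reading.
- Given criterion 30, joint criterion 15 adds one exclusion: the fifth row.
- Letting AST also be above or within 2xULN gives 2 x 6 = 12 combinations. Again exactly 1 changes between the readings, the same pattern with AST within limits, because AST >2xULN excludes by itself.

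**What follows in the differing pattern (Appendix 2; bilirubin is ≤1.5xULN at entry).**
- ALT >2 to <3xULN: no monitoring or stopping threshold is met.
- ALT 3 to <5xULN, no symptoms, bilirubin <2xULN: treatment may continue under weekly monitoring. It stops if ALT ≥3xULN persists for at least 4 weeks or another stopping row is met.
- ALT ≥5xULN, which is 5/2 = 2.5 times the criterion 15 figure: immediate discontinuation.

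**The case against.** The joint reading can be defended as coherent. Criterion 30 lets in raised bilirubin with a direct fraction below 35%, and joint criterion 15 takes that subject out again when ALT is also raised. The parenthesis then merely restates that such bilirubin is acceptable when isolated, which makes it redundant rather than contradictory. It can also be said that if the parenthesis points sites to the stricter reading, little practical risk remains.

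Other safeguards narrow the gap. The worst case needs ALT ≥5xULN with AST ≤2xULN and with ALP and bilirubin within limits. Criterion 16 could reasonably be taken to cover a confirmed high ALT, hepatitis B and C serology and alcohol abuse are excluded separately, and Section 7.2 permits randomisation without obliging it. Chemistry is repeated pre-dose on Day 0 and again from Week 4, so Appendix 2 would catch a missed subject, though possibly after the first doses. Finally, the pattern counts are not frequencies.

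Much of this stands as a limit on size: the serious consequence is confined to ALT ≥5xULN, and the number affected is unknown. It does not remove the defect. If the joint rule was meant, ALT alone has no numeric limit while AST, ALP and bilirubin each have one, and the exception is surplus. If separate limits were meant, the conjunction is wrong. Criterion 16 and investigator judgement state no threshold, so sites may still differ.

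**Conclusion.** The concern holds: criterion 15 is wrong as written. Followed literally, criteria 15 and 30 admit a raised ALT at any level when bilirubin, AST and ALP are within limits, and the isolated-bilirubin exception has no effect. The two readings differ in 1 of 6 patterns (3 against 4 excluded). Within that pattern, only ALT ≥5xULN puts a subject at the immediate-stopping threshold at entry; from 3 to <5xULN the usual consequence is weekly monitoring.

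This assumes that the subject is not excluded under criterion 16 or by the investigator. The counts describe the logic of the rules and say nothing about how common the pattern is, which the protocol does not allow one to estimate. Sample size, power and alpha are unaffected. The issue is subject safety and consistent eligibility decisions across sites.

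**What to change.** Either of two edits will do:

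1. In criterion 15, replace *and* with *or* between the ALT and bilirubin limits and keep the exception for isolated bilirubin.
2. Add ALT >2.0 times the upper limit of normal beside AST in criterion 30 and delete criterion 15, whose bilirubin rule criterion 30 already contains.

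Both exclude the same 4 of 6 patterns. The second is tidier, since all four liver tests then sit in one list. If the sponsor really means a joint rule, the exception should be deleted and the absence of an ALT limit justified.

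The cost is one word or one bullet, plus possibly some screen failures beyond those Section 4.4 already allows for (94 screened for about 70 randomised, so 94 − 70 = 24). The extra number cannot be derived from the protocol but is likely to be small, because AST >2xULN already excludes by itself.

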5.3. Screening/Baseline/Run-in Failures

Screen failures are defined as subjects who consent to participate in the clinical trial but are never subsequently randomized. In order to ensure transparent reporting of screen failures meet the Consolidated Standards of Reporting Trials publishing requirements, and respond to queries from Regulatory authorities, a minimal set of screen failure information is required including Demography, Screen Failure details, Eligibility Criteria, and any Serious Adverse Events.

Rescreening: Subjects who fail screening may be rescreened once at the discretion of the investigator.

Repeat assessments during the 35 day screening period: assessments (see Section 7.1), including laboratory assessments, may be repeated if determined necessary by the investigator, for example: (a) in cases of technical malfunction (e.g., loss of laboratory specimen), (b) in the event of a value close enough to the exclusionary threshold that it may reasonably lie within the degree of variability of the assay; (c) if there is reason to believe the result may be false (i.e.: contradicts recent result for the same parameter). These are repeat assessments and not rescreening events. If the original result was exclusionary and is confirmed by repeat testing, the subject will be excluded.

In the specific case of an indeterminate result from autoantibody (SS-A, SS-B) assessment during the 35 day screening period, this assessment may be repeated once. If the result from the repeat assessment is either indeterminate or negative, the subject will be excluded.

5.4. Withdrawal/Stopping Criteria

5.4.1. General Criteria

The following actions must be taken in relation to a subject who fails to attend the clinic for a required study visit:

- The site must attempt to contact the subject and re-schedule the missed visit as soon as possible.
- The site must counsel the subject on the importance of maintaining the assigned visit schedule and ascertain whether or not the subject wishes to and/or should continue in the study.
- In cases where the subject is deemed ‘lost to follow up’, the investigator or designee must make every effort to regain contact with the subject (where possible, 3 telephone calls and if necessary a certified letter to the subject’s last known mailing address or local equivalent methods). These contact attempts should be documented in the subject’s medical record.
- Should the subject continue to be unreachable, only then will he/she be considered to have withdrawn from the study with a primary reason of “Lost to Follow-up”.

A subject may withdraw from study treatment at any time at his/her own request, or may be withdrawn at any time at the discretion of the investigator for safety, behavioral or

administrative reasons. If a subject withdraws from the study, he/she may request destruction of any samples taken, and the investigator must document this in the site study records.

If a subject experiences a clinically significant AE that the investigator believes may be definitely, possibly or probably related to study agent and could potentially be exacerbated by the next dose, the investigator may delay IP dosing by up to one week or withhold one dose (or single dose co-administration). If a similar concern is present at the time of the next scheduled dose, the investigator should contact the Medical Monitor to determine whether treatment with belimumab or rituximab should be discontinued.

Subjects who discontinue IP (i.e., during the treatment phase prior to Week 52) should be encouraged to continue to participate in study visits in accordance with the Time and Events schedule, especially all remaining safety evaluations. All subjects, including those who decline to complete the treatment phase visits through Week 52, are required to participate in the general follow up phase (and the individualized follow up phase, if applicable).

In addition, for a subset of subjects who receive rituximab/placebo at the Week 8 visit, or at both the Weeks 8 and 10 visits, but who discontinue treatment prior to Week 46, maintenance of contraception and monthly telephone calls for urine pregnancy test results will be required until approximately 52 weeks after the last dose of rituximab/pbo was administered.

Week 46 is an important threshold for withdrawal as it is only beyond week 46 that continued exposure to belimumab/placebo dictates a longer follow up for pregnancy evaluation (Section [7.4.2](#)).

Subject discontinues treatment before the Week 8 Visit	Subject discontinues treatment after the Week 8 Visit and before Week 46	Subject discontinues treatment at or after Week 46

 ➤ General follow-up visit 16 weeks after last dose of IP ➤ Monthly telephone calls for urine pregnancy test results, neurological questionnaire, AEs, SAEs, and concomitant medications during the 16-week general follow-up period ➤ Individualized safety follow-up visits every 12 weeks subsequent to the general follow up period (if applicable) 	
 ➤ General follow-up visit 16 weeks after last dose of IP ➤ Monthly telephone calls for urine pregnancy test results, neurological questionnaire, AEs, SAEs, and concomitant medications during the 16-week general follow-up period. ➤ maintenance of contraception and monthly telephone calls for urine pregnancy test results will be required until approximately 52 weeks after the last dose of rituximab/pbo was administered. ➤ Individualized safety follow-up visits every 12 weeks subsequent to the general follow up period (if applicable) 	
 ➤ General follow-up visit 16 weeks after last dose of IP ➤ Monthly telephone calls for urine pregnancy test results, neurological questionnaire, AEs, SAEs, and concomitant medications during the 16-week general follow-up period. ➤ Individualized safety follow-up visits every 12 weeks subsequent to the general follow up period (if applicable)

Please refer to Section 5.4.4 of the study reference manual for further consideration of scenarios which may be encountered in terms of the timing and circumstances of subject withdrawal and the steps which need to be followed.

